### **5.2.1. Product Characteristics**

Relugolix has no chiral centers. The compound is slightly to partially soluble in acidic solutions but essentially insoluble at neutral pH (pH 7) and above. It is partially soluble in polar organic solvents. The compound is provided as an immediate-release pink tablet using common excipients.

The fixed-dose combination tablet of estradiol 1.0 mg and norethindrone acetate 0.5 mg is encapsulated in a gelatin capsule with sufficient common back-fill material.

### **5.3. Randomization and Stratification**

This extension study is a single-arm, open-label study, and thus, patients are not randomized or stratified upon enrollment in this study.

### **5.4. Directions for Administration**

All study patients will take a study treatment of one tablet and one capsule once daily.

The study treatment should be taken in the fasted state (other than water, tea, or coffee) in the morning, at least 1 hour before breakfast. If dosing is missed in the morning for any reason, the study treatment may be taken later in the day, under fasting conditions, at least 1 hour before or 2 hours after eating a meal. The study treatment should be taken as close as possible to the same time of morning each day.

On Week 24/Baseline and Week 52 clinic visit days, study drug will be administered in the clinic rather than at home (see Schedule of Activities in [Section 1.1](#)).

### **5.5. Dose Reduction/Dose Administration**

No toxicity-related dose reductions of study drug are permitted. Patients who experience a grade 3 or greater toxicity that cannot be ameliorated by the use of adequate medical intervention should have their treatment interrupted until the toxicity improves to a grade 2 or lower severity. Patients may subsequently be re-started on study drug with the written approval of the sponsor (or designee).

### **5.6. Storage, Packaging, and Labeling**

Study drug should be stored in an appropriate, limited-access, secure location at room temperature. Follow storage conditions described on the drug labeling. Study drug should be stored protected from light. A daily temperature log of the drug storage area must be maintained every working day. Study drug must be stored under the conditions specified on the label, and remain in the original container until dispensed. Only patients enrolled in the study may receive study drug, and only authorized site staff may supply or administer study drug. Further guidance and information for final disposition of unused study drug are provided in the Study Reference Manual and Pharmacy Manual. The investigator is responsible for study drug accountability,

reconciliation, and record maintenance, including receipt, reconciliation, and final disposition records and their secure storage.

Study drug will be labeled with the study protocol number, medication or lot/batch number, contents, directions for use, storage directions, clinical study statement, and any other labeling required by regulatory bodies in the study locations and will list Myovant Sciences GmbH as the sponsor. Patients will be instructed to store study drug at room temperature out of the reach of children.

All labels for relugolix and the estradiol/norethindrone acetate combination to be distributed will meet all applicable requirements of the US Food and Drug Administration (FDA) and Annex 13 of Good Manufacturing Practices: Manufacture of investigational medicinal products (July 2010) and/or other local regulations as applicable.

Please see [Appendix 1](#) for a list of protocol-specified analgesics. Further details on analgesic medication are provided in the Study Reference Manual.

## 5.7. Rescue Analgesic Medications

Management of endometriosis-associated pain often requires treatment with analgesics and some patients require treatment with opioid drugs. Two tiers of pain medications are specified for this trial. The study-specified pain medications for each patient will be the same as for the parent study. Only study-specific Tier 1 and Tier 2 analgesic medications (see [Appendix 1](#)) should be taken starting with the Baseline/Week 24 visit and subsequently. Analgesic medications will be taken for control of pain and not prophylactically.

If a patient develops uncontrolled endometriosis-associated pain during the study despite use of the study-specified analgesics or an intolerance to a study-specified analgesic, please contact the medical monitor.

Short-term use of non-study specified analgesics for the treatment of an intercurrent event (eg, injury or surgery) is allowed, if required. Such events should be reported as adverse events.

Investigators must instruct the patient on the use of ibuprofen 200 mg tablets (ie, number of tablets per dose, dosing frequency, maximum number of tablets per day). For patients who may need the Tier 2 analgesic medication, a prescription should also be written for this at the time of enrollment into this study. This is to ensure that patients do not endure unnecessary pain during the conduct of the study.

Quantities of opioids prescribed should be based on the patient's expected usage until the next study visit. Prescriptions for Tier 1 and Tier 2 rescue analgesic medications should be in accordance with their full prescribing information (ie, the local product labeling) and prescriptions for opioids should not provide for any refills. Patients should be counseled on the safe use of opioids.

Patients who are not prescribed the Tier 2 medication at the time of enrollment in this study, for example, because requirement for analgesics beyond the Tier 1 medication is not expected (eg, based on pain level and/or recent analgesic requirements) should be advised to contact the investigator if pain is inadequately controlled with the Tier 1 medication alone. To avoid experiencing extended periods of uncontrolled pain, patients who require the Tier 2 medication

should get a prescription from the investigator and initiate treatment with the Tier 2 medication as soon as feasible.

Use of protocol-specified rescue analgesic medications and any other analgesics taken for any type of pain, must be recorded by the patient in the e-Diary.

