### **5.10.3. Prohibited Non-Drug Therapies**

Surgical treatment of endometriosis is prohibited from the Week 24/Baseline visit until the patient's final study visit unless urgently needed for patient safety.

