### 7.1. Adverse Event Definitions

#### 7.1.1. Adverse Event

Adverse event: An adverse event is any unfavorable and unintended sign (including an abnormal laboratory finding), symptom, or disease (new or exacerbated) temporally associated with the use of a medicinal product, whether or not related to the medicinal product.

Events meeting the definition of an adverse event **include**:

- A worsening, excluding minor fluctuations, in the nature, severity, frequency, or duration of a pre-existing condition;
- Development of an intercurrent illness during the study;
- Development of symptoms that may or may not be related to the use of a concomitant medication or investigational product;
- Injury or accidents: If a medical condition is known to have caused the injury or accident, the medical condition and the accident should be reported as 2 separate medical events (eg, for a fall secondary to dizziness, both “dizziness” and “fall” should be recorded separately); and
- An investigational abnormality (eg, laboratory parameter, vital sign, ECG) only if the abnormality is considered clinically significant by the investigator based on at least one of the following criteria:
  - Induces clinical signs or symptoms;
  - Requires active intervention;
  - Requires interruption or discontinuation of study drug.

Events that **do not** meet the definition of an adverse event include:

- Medical or surgical procedures (eg, surgery, endoscopy, tooth extraction, transfusion); the condition that leads to the procedure is an adverse event;
- Pre-existing diseases or conditions present or detected before the start of study drug administration that do not worsen;

- Situations where an untoward medical event has not occurred (eg, planned hospitalization for an elective procedure, with elective defined as known or planned at the time of signing of the informed consent);
- Endometriosis-associated pain is not considered an adverse event in this study because it is being quantitatively measured as the primary efficacy endpoint.

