### 7.1.2. Serious Adverse Event

A serious adverse event is any untoward medical occurrence that, at any dose:

- a. Results in death;
- b. Is life-threatening;  
NOTE: The term “life-threatening” in the definition of “serious” refers to an event in which the study participant was at risk of death at the time of the event. It does not refer to an event, which hypothetically might have caused death, if it were more severe. For example, drug-induced hepatitis that resolved without evidence of hepatic failure would not be considered life-threatening even though drug-induced hepatitis can be fatal.
- c. Requires hospitalization or prolongation of existing hospitalization;  
NOTE: In general, hospitalization signifies that the patient has been admitted to a hospital, independent of the duration of that hospitalization. Complications that occur during hospitalization are adverse events. If a complication prolongs hospitalization or fulfills any other serious criteria, the event is serious. When in doubt as to whether “hospitalization” occurred or was necessary, the adverse event should be considered serious. Hospitalization for elective treatment of a pre-existing condition that did not worsen from baseline is not considered an adverse event.
- d. Results in persistent or significant disability/incapacity;  
NOTE: The term disability means a substantial disruption of a person’s ability to conduct normal life functions. This definition is not intended to include experiences of relatively minor medical significance such as uncomplicated headache, nausea, vomiting, diarrhea, influenza, and accidental trauma (eg, sprained ankle) which may interfere or prevent everyday life functions but do not constitute a substantial disruption.
- e. Is a congenital anomaly/birth defect;
- f. Important medical events which jeopardize the patient and may require medical or surgical intervention to prevent one of the outcomes listed above. Examples of such events are invasive or malignant cancers, intensive treatment in an emergency room or at home for

---

allergic bronchospasm, blood dyscrasias or convulsions that do not result in hospitalization, or development of drug dependency or drug abuse.

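### Amendment 1 tells sites in Section 5.7 to report surgery as an adverse event, while Section 7.1.1 says surgery is not one; the two need reconciling

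*Protocol*

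**What the plan says.** Section 5.7 (Rescue Analgesic Medications) is new in Protocol Amendment 1. It permits short courses of analgesics other than the study-specified ones for "an intercurrent event (eg, injury or surgery) is allowed, if required. Such events should be reported as adverse events". Footnote 1 to Table 5-2 sends sites to this section when they ask whether a non-study analgesic may be used.

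Section 7.1.1 of the same version has a list headed "Events that do not meet the definition of an adverse event include". Its first entry is "Medical or surgical procedures (eg, surgery, endoscopy, tooth extraction, transfusion); the condition that leads to the procedure is an adverse event". A later entry covers situations with no untoward event, with the example "planned hospitalization for an elective procedure, with elective defined as known or planned at the time of signing of the informed consent". The same list leaves out pre-existing conditions that do not worsen. Injuries, by contrast, are on the list of things that are adverse events ("Injury or accidents: If a medical condition is known to have caused the injury or accident").

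Section 7.1.2 makes an event serious if it "Requires hospitalization or prolongation of existing hospitalization", but the note to that criterion says "Hospitalization for elective treatment of a pre-existing condition that did not worsen from baseline is not considered an adverse event".

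**The concern.** Section 5.7 gives two examples of what is to be reported as an adverse event, and one of them is something Section 7.1.1 says is not an adverse event. Neither section refers to the other on this point, and the text shown contains no rule on which takes precedence.

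Adverse event incidence is a named safety endpoint. Section 9.5 tabulates it by system organ class and preferred term, by relationship and by severity. With approximately 320 sites, a site that follows 5.7 may enter an operation as an adverse event while a site that follows 7.1.1 does not, or enters the condition instead. The tables would then partly reflect which section a site read.

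**Working it through.** No arithmetic applies. The check sets the Amendment 1 rules side by side for each kind of event.

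1. **Injury.** Section 5.7: adverse event. Section 7.1.1: adverse event. They agree, so only the surgery half of the 5.7 example needs repair.

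2. **Operation prompted by a new or worsened condition.** Section 5.7, read literally: the operation is reported. Section 7.1.1: the operation is not an adverse event, but the condition behind it is. Either way there is something to report. What can differ is the term, procedure or condition, and hence the preferred term and possibly the system organ class. A site that enters both adds a record.

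3. **Operation for a pre-existing condition that has not worsened.** Section 5.7, read literally: one adverse event. Section 7.1.1: none, because the procedure and the unworsened condition are both excluded, as is an admission already planned at consent. The note in 7.1.2(c) agrees. This is the only case in which the difference is one record versus none.

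4. **Seriousness.** Section 5.7 does not mention it. For an elective admission to become a serious adverse event, the 5.7 sentence would have to make the operation an adverse event despite 7.1.1 and also displace the note in 7.1.2(c). Nothing in the text says that it does either.

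5. **Role of the analgesic.** The second 5.7 sentence refers back to intercurrent events. It can be read as covering those for which a non-study analgesic was used, or intercurrent events in general. On the first reading the choice of analgesic affects reporting; on the second it does not. The conflict with 7.1.1 on surgery exists on both readings.

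6. **Origin.** The 7.1.1 exclusion of procedures already stands in the original protocol. The Amendment 1 summary of changes describes the relevant part of 5.7 as an allowance for short-term analgesics and mentions no change to adverse event definitions. That suggests a slip in drafting, not a deliberate new reporting rule.

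**The case against.** The strongest reply is that the two sections can be read together. An operation planned before consent is not naturally intercurrent, and 7.1.1 itself counts intercurrent illness and injury as adverse events. For unplanned surgery, 7.1.1 already yields an adverse event through the underlying condition, and Section 7.2 asks for a diagnosis as the term where one is available. A site working from Section 7 would normally record the condition. That sites would in fact diverge is an inference; the documents contain no evidence of it.

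The affected group is also narrow. Inclusion criterion 3 keeps out women expected to have gynecological surgery or surgery for endometriosis, and Section 5.10.3 adds "Surgical treatment of endometriosis is prohibited from the Week 24/Baseline visit until the patient's final study visit unless urgently needed for patient safety". The conflict therefore mainly concerns other operations, and many of those may be covered by the study analgesics already available.

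These points limit the size of the effect, but they do not remove the contradiction. Surgery is one of only two examples in the 5.7 sentence, and a reader sent there from Table 5-2 has no pointer to 7.1.1.

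A reader might go further and infer that a planned operation becomes a serious adverse event needing a 24-hour report. The documents do not support that: 5.7 says nothing about seriousness, and both 7.1.1 and the 7.1.2(c) note specifically exclude elective cases. A reader might also infer that the painkiller alone decides whether an operation counts. That is only one reading of the sentence; 5.7 does not say that an event treated with study analgesics goes unreported.

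**Conclusion.** The contradiction is real, within a single protocol version, and limited to surgery. For an operation on an unworsened pre-existing condition, the classification is left open between one adverse event and none. For surgery prompted by a new or worsened condition, mainly the reported term is at risk. The number of such operations is not given, so the effect on adverse event incidence cannot be calculated. It is probably small, and any error tends towards over-reporting. No efficacy result, sample size or precision statement depends on it.

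This conclusion assumes that some sites take the 5.7 sentence at its word. It applies to Amendment 1. Amendment 2's table of contents still lists a Section 5.7 with the same title, but its text is not shown, nor are Amendments 3 and 3.1. The point therefore cannot be stated as a defect of the final protocol.

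**What to change.** Replace the last sentence of that paragraph in Section 5.7 with a reference to the definitions, for example: *The underlying condition or injury is assessed and reported according to Section 7.1.1; the procedure itself is not an adverse event.* This leaves the permission to use analgesics as it is and changes only how the event is reported.

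Add a data-cleaning check that queries any adverse event record containing only a procedure term, so that the site can supply the condition or confirm that there was none. Querying is preferable to excluding such records from the safety tables, because exclusion would drop investigator-reported events without clarification.

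Check whether the sentence persists in Amendments 2, 3 and 3.1, and correct it there if so. The cost is one sentence and one query rule; adverse event counts may fall slightly and some terms may change from procedure to condition.

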## **5.8. Blinding**

Blinding is not applicable for this open-label extension study.

## **5.9. Study Drug Accountability and Treatment Compliance**

Patients should complete their eDiary each day on study and should bring all unused and used study drug to each study visit. At the Week 24/Baseline visit and Week 52/ET visit, all used and unused study drug kits should be retained at the site. New study drug should be dispensed as described in [Section 1.1](#) (Schedule of Activities). At all other visits, only used study drug kits should be retained at the site.

Study drug accountability will be conducted and results will be recorded. If a patient is persistently noncompliant with the study treatment, it may be appropriate to withdraw the patient from the study (see [Section 4.5](#)). All patients should be reinstructed about the dosing requirement during study contacts. The authorized study personnel conducting the re-education must document the process in the patient's source records.

Because of the importance to both safety and efficacy evaluation, patients who are grossly noncompliant with eDiary completion must undergo an Unscheduled visit to evaluate reasons for noncompliance and to develop a plan to improve compliance. Failure to improve compliance may result in the sponsor withdrawing the patient from further study treatment (including study analgesics) and/or discontinuation from the study (see [Section 4.5](#) for details).

All patients should be reinstructed about the dosing requirement and eDiary compliance during study contacts. The authorized study personnel conducting the re-education must document the process in the patient's source records.

## **5.10. Prior and Concomitant Medications and Non-Drug Therapies**

### **5.10.1. Prohibited Medications**

[Table 5-2](#) provides examples of prohibited drug categories; however, it is not a comprehensive list of all restricted medications. Drugs and drug classes in [Table 5-2](#) are prohibited at any time during the study through the Follow-Up visit, except as noted in the table. Consult the medical monitor if there is any uncertainty regarding patient use of a particular drug or drug class.

**Table 5-2 Prohibited Medications**

Drug Class	Examples	Comments
Bisphosphonates	alendronate etidronate zoledronic acid	
GnRH analogues	leuprolide acetate injection, also known as leuprorelin goserelin acetate injection	
Anti-androgens	danazol	
Anticonvulsant drugs (specified)	phenobarbital carbamazepine phenytoin valproic acid primidone	Note: All other anticonvulsants are allowed
Aromatase inhibitors	anastrozole letrozole	
Progestins and progestin implants	dienogest norethindrone medroxyprogesterone cyproterone etonogestrel	
Estrogens	estradiol valerate conjugated estrogens ethynyl estradiol	
Hormonal contraceptives, contraceptive patches and vaginal rings	combined or progestin only NuvaRing	
Selective estrogen receptor modulators	raloxifene bazedoxifene lasofoxifene clomifene tamoxifen	
Selective progesterone receptor modulators	mifepristone ulipristal acetate	
Over-the-counter and herbal products/teas with known hormonal activity	plant-based estrogen products “natural” thyroid supplements dihydroepiandrosterone (DHEA)	
Intrauterine devices	levonorgestrel copper	

Drug Class	Examples	Comments
Bone agents	calcitonin calcitriol ipriflavone teriparatide denosumab abaloparatide odanacatib romosozumab	Calcium and Vitamin D2 and Vitamin D3 (ergocalciferol and cholecalciferol) are allowed without restriction.
Glucocorticoids	prednisolone or prednisone dexamethasone	Anticipated use of systemic glucocorticoids at an oral prednisone-equivalent dose of more than 5 mg every other day during the study.  Note: topical, inhaled, intranasal, otic, ophthalmic, intraarticular, or intralesional subcutaneous are permitted without restriction.  Short duration (< 21 days) higher-dose glucocorticoids required for acute events are permitted during the study.
P-glycoprotein inducers	avasimibe carbamazepine phenytoin rifampin St. John's wort tipranavir/ritonavir f	Note: For patients requiring a short course of these drugs during the study, investigator must contact the medical monitor for approval and guidance on study drug administration during this period.

Drug Class	Examples	Comments
Moderate and strong P-glycoprotein inhibitors	amiodarone azithromycin a captopril b carvedilol clarithromycin a conivaptan cyclosporin c diltiazem dronedarone erythromycin a felodipine d itraconazole e ketoconazole e lopinavir/ritonavir f quercetin quinidine ranolazine ticagrelor g verapamil	Note: For patients requiring a short course of these drugs during the study, investigator must contact the medical monitor for approval and guidance on study drug administration during this period.
Analgesic drugs other than those specified for use during the study 	Acetaminophen/paracetamol (other than any included in a study-specified analgesic) aspirin > 325 mg/day NSAIDs (other than study-specified NSAIDs) gabapentin pregabalin carbamazepine metamizole	Note: Aspirin ≤ 325 mg per day is allowed
Antidepressants New treatment or changed doses of SSRI, SNRI, or TCA antidepressants	SNRI examples: duloxetine venlafaxine desvenlafaxine SSRI examples: citalopram fluoxetine paroxetine fluvoxamine TCA examples: amitriptyline doxepin desipramine nortriptyline	SSRI, SNRI, or TCA allowed if given at the same dose as used during the 3 months prior to the Run-In Period of MVT-601-3101 or MVT-601-3102.  New start, dose change or discontinuation of these drugs is not allowed during the study. Changes made for safety reasons are allowed with approval of the medical monitor.

Abbreviation: GnRH, gonadotropin-releasing hormone; NSAID, nonsteroidal anti-inflammatory drug; SNRI, serotonin and norepinephrine reuptake inhibitor; SSRI, selective serotonin reuptake inhibitor; TCA, tricyclic antidepressant.

For situations where non-study analgesics may be allowed, see [Section 5.7](#)

- a. Roxithromycin is allowed
- b. All other angiotensin converting enzyme inhibitors are allowed
- c. Tacrolimus is allowed
- d. Amlodipine and nifedipine are allowed
- e. Fluconazole is allowed
- f. Integrase inhibitors are allowed
- g. Clopidogrel is allowed

